8.1 Sample Size

The sample size of 210 subjects who undergo implantation and exchange of a Travoprost Intraocular Implant was determined empirically. This sample size is considered adequate to provide information on the safety of the exchange procedure.

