9.1 Serious Adverse Event

Serious adverse events are defined as any findings that suggest a significant hazard, contraindication, side effect, or precaution. Any adverse event is considered a serious adverse event if it results in any of the following outcomes:

- Death
- Life- or sight-threatening
- Overnight hospitalization or prolongation of an existing hospitalization
- A persistent or significant disability/incapacity
- A congenital anomaly/birth defect

CLINICAL PROTOCOL

Date: September 18, 2019	Protocol No.: IDOS-402-IVIV
-----------------------------	--------------------------------

The terms “mild,” “moderate,” and “severe” are measures of intensity; thus a severe AE is not necessarily serious. For example, nausea of several hours duration may be rated as severe but may not be clinically serious.

Important medical events that may not result in death, be life-threatening, or require overnight hospitalization may be considered a serious adverse drug experience when, based upon appropriate medical judgment, they may jeopardize the subject and may require medical or surgical intervention to prevent one of the outcomes listed above. A life-threatening event is any event that places the subject at substantial risk of death from the event as it occurred; it does not refer to an event that hypothetically might have caused death if it were more severe. A sight-threatening event is any event that places the subject at risk of permanently losing vision in either eye as a direct result of the event.

Serious adverse events must be reported to Glaukos immediately (preferably within 24 hours of knowledge of the event).

When new significant information (including the outcome of the event) is obtained, the investigator should inform Glaukos as soon as possible. Depending on the nature of the AE, Glaukos may request copies of the ophthalmic and medical records of the subject. If the subject was hospitalized for a study-treatment related serious adverse event, a copy of the discharge summary must be forwarded to Glaukos as soon as possible.

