7.1.2. Adverse Events

Adverse events (AEs) will be coded to the MedDRA nomenclature, Version 21.0. Treatment Emergent Adverse Events (TEAEs) are defined as AEs that occur after the initiation of the first surgery at Visit 2 (First Operative Day 0).

AEs will be categorized into either the initial or PE study periods, as described in Section 2.3.1. AEs that extend between study periods (i.e., beginning during the initial study period and extending into the PE study period), will be categorized into the initial study period. However, if an increase in severity or change in relationship to study treatment occurs during the PE study period, the AE will be categorized into both the initial and PE study periods.

A summary of the number and percentage of subjects with TEAEs [REDACTED] will be provided for each study period. The summary will include study eye TEAEs, non-ocular or non-study eye TEAEs, treatment-related TEAEs, TEAEs by maximum severity, TEAEs resulting in study discontinuation, serious TEAEs, and deaths.

The number and percentage of subjects with study eye TEAEs, non-study eye TEAEs, and non-ocular TEAEs will be provided by SOC, PT, [REDACTED] for:

- TEAEs
- TEAEs related to study treatment
- TEAEs by maximum severity
- Serious TEAEs

Tabulations of study eye TEAEs for each of the above categories will be provided for each study period.

All AEs will be presented in a listing by subject. Separate listings for intraoperative AEs, serious adverse events (SAEs), AEs leading to deaths, AEs leading to study discontinuation, and AEs leading to removal of implant will also be presented.

Relationship to study treatment is defined as the possibility that the study treatment caused the event and is described in the study protocol. The relationship to study treatment categories utilized on the CRF are definitely unrelated, unlikely related, possibly related, probably related, and definitely related. For all tabulations presenting relationship to study treatment, the categories of possibly related, probably related, and definitely related will be classified as related and only related AEs will be presented. AEs with missing relationships are counted as related. Subjects experiencing more than one treatment related AE within a given SOC or PT will be counted once within that SOC or PT.

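### The SAP's rule for AEs that span the exchange ignores an event becoming serious, so the post-exchange serious-TEAE tables can under-count.

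*SAP*

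**What the plan says.** SAP 2.3.1 divides the data at Visit 7. The PE period holds what is collected during and after the exchange procedure.

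For AEs, SAP 7.1.2 sets a default: an AE "beginning during the initial study period and extending into the PE study period), will be categorized into the initial study period". The only exception is that "if an increase in severity or change in relationship to study treatment occurs during the PE study period, the AE will be categorized into both" periods.

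The same section reports by period. The overview for each period includes "TEAEs by maximum severity, TEAEs resulting in study discontinuation, serious TEAEs, and deaths". The SOC/PT categories are all TEAEs, related TEAEs, TEAEs by maximum severity and serious TEAEs, and "Tabulations of study eye TEAEs for each of the above categories will be provided for each study period".

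Severity has three grades. The CRF relationship categories are "definitely unrelated, unlikely related, possibly related, probably related, and definitely related". In relationship tables the upper three "will be classified as related and only related AEs will be presented".

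Protocol 9.1 defines seriousness by outcome and warns that "a severe AE is not necessarily serious". On sample size, Protocol 8.1 says: "This sample size is considered adequate to provide information on the safety of the exchange procedure".

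**The concern.** The SAP tabulates seriousness by period but does not let seriousness decide the period. Severity cannot stand in for it, because the protocol treats the two as separate attributes. Take an event that starts before the exchange at moderate grade, possibly related, and after the exchange leads to an overnight hospitalization with both ratings unchanged. It meets neither trigger, so it stays in the initial period and is missing from the PE serious-TEAE tables.

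The PE tables are where a reader will look for harm from the exchange, and the protocol offers the sample size as informative on exactly that. A serious event placed against the first implantation weakens that reading.

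The relationship trigger has a smaller defect. Severity must increase, but relationship need only change. An event re-rated after the exchange from possibly related to definitely unrelated is added to the PE all-causality count although nothing about it has worsened.

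**Working it through.** The documents state no figure that depends on this rule, so there is nothing to reproduce. The check is to write the rule out and list the patterns it captures. These are counts of possible patterns, not expected frequencies.

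**Inputs.** Severity grade S (3 levels), relationship R (5 levels), serious yes/no (SAP 7.1.2; Protocol 9.1). Subscript 1 is before the exchange, 2 is after. The planned size is 210, as 14 cohorts of 15 (section 2.3 of the data analysis plan issued with the SAP).

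**Rule as written.** Count in PE if S₂ > S₁ or R₂ ≠ R₁. Seriousness does not appear.

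**Newly serious events.**
- Patterns going from non-serious to serious: (3 × 5) × (3 × 5) = 225.
- Missed when severity does not rise and relationship is unchanged. Severity pairs without a rise: 3 equal + 3 lower = 6. Unchanged relationship: 5. Missed: 6 × 5 = 30, of which 15 have the same grade and 15 a lower grade.
- Captured: 225 − 30 = 195.

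**Relationship trigger.**
- Possible changes: 5 × 4 = 20, of which 10 go up and 10 go down. All 20 trigger.
- Not related to related: 2 × 3 = 6. Related to not related: 6. Within one class: 2 × 1 + 3 × 2 = 8.
- Patterns counted in PE on a downgrade alone: 6 (severity not rising) × 10 (relationship down) × 3 (not newly serious, out of 4 before/after pairs) = 180.

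**Scale of one misplaced subject.**
- 1/210 = 0.48%; 1/15 = 6.7%.
- Exact two-sided 95% upper limit: 0/210 gives 1 − 0.025^(1/210) = 1.74%; 1/210 gives 2.62%.
- These limits assume that all 210 subjects reach the exchange. They are not planned outputs and only illustrate scale.

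**The case against.** A reader might infer that the PE tables are wrong. The documents do not support that. An error needs an AE that starts before the exchange, is still open at it, first becomes serious in the roughly four weeks that follow, and shows neither a severity increase nor a relationship change. No AE rates are given, and such events are likely to be rare. An event that becomes serious together with either trigger is captured.

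It can be said that data collection may solve the problem. Protocol 9 treats a clinically significant change after treatment as an AE, so an event turning serious might be entered as a new record with onset in the PE period. The CRF is not in the documents, so this cannot be ruled out, and a new record would close the gap. But the SAP's own triggers presuppose that severity and relationship are tracked within one ongoing AE. Neither document says that seriousness is handled differently.

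It can also be said that nothing is hidden, because every SAE appears in a listing that does not depend on the period rule and the total-period serious count is right. That stands, but neither corrects a PE table that shows too few serious events.

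On the downgrade, the objection is largely right. The event stays in the initial period as well, and over-counting in the PE period is the cautious direction. The PE table of related events need not be inflated if the post-exchange rating is used, although the SAP does not say which rating applies.

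Finally, it would be too strong to say that the trial was sized for exchange safety. Protocol 8.1 calls the size empirical, and SAP 2.4 says that it supports the study objectives without a power calculation.

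**Conclusion.** The concern holds as a defect in a stated rule with a conditional effect. Followed exactly, SAP 7.1.2 leaves an AE that becomes serious after the exchange, at unchanged grade and relationship, out of the PE serious-TEAE overview and study-eye table. It shows that event as serious in the initial period. Those PE tables can under-count; the documents do not show that they will.

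This assumes that seriousness is updated on the existing AE record, as the SAP's wording implies for severity and relationship. The number of events affected cannot be estimated, but the tables are small enough for a single serious event to be visible.

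The undirected relationship trigger is secondary. It can add events to the all-causality PE count but removes none from the initial period. A related omission is that the SAP does not say which period's severity, relationship or seriousness is shown for an AE counted in both, so two programmers could produce different tables. The whole is worth an amendment before database lock.

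**What to change.** In SAP 7.1.2:

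1. Add to the triggers for PE counting: *or the AE first meets a seriousness criterion during the PE study period*. All 225 newly serious patterns would then be captured.
2. State that each period's table uses the severity, relationship and seriousness that held in that period.
3. Optionally, give the relationship trigger a direction, as any upward change on the five-category scale. The 180 downgrade-only patterns would then leave the PE count. Do not restrict it to a move from not related to related. That would keep only 6 of the 10 upward changes and drop the three upgrades within the related class (possibly to probably, possibly to definitely, probably to definitely), which the present rule captures and which could reflect the exchange.

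The cost is a short amendment, which SAP section 1 allows before database lock, and a small change to the AE derivation. The date on which seriousness was first met is also needed. The documents do not show whether the CRF records it, but the present rule already needs dated changes in severity and relationship.

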2.3. Study Design

This is a prospective, non-randomized, open-label, single center trial evaluating [REDACTED]
[REDACTED] the performance of the Travoprost Intraocular Implant in subjects with open-angle glaucoma (OAG) or ocular hypertension (OHT). Approximately 210 total subjects [REDACTED] will be enrolled into the study. Subjects will be screened for qualification as per the inclusion/exclusion criteria (refer to Sections 6.2.1 and 6.2.2 of study protocol). Qualified subjects will be assigned to a cohort and will be implanted with the Travoprost Intraocular Implant (G2-TR-125 Implant) in one eye. [REDACTED]
[REDACTED]
[REDACTED]

[figure not shown]
[REDACTED] All enrolled subjects will undergo a second operative visit, the exchange of the Travoprost Intraocular Implant, at Visit 7. The duration of time for each cohort is the time between the implantation of the 1st implant at Visit 2 (Day 0) and the implantation of the 2nd implant at Visit 7 (Exchange procedure). Depending on the cohort assignment, subjects will be follow for 4 – 25 months postoperatively (3 – 24 months after 1st implantation and 4 weeks after the 2nd implantation). Study follow-up will continue until the Week 4 PE visit.

Depending on the cohort assignment, the study consists of 10 to 13 visits: Visit 1 (Screening), Visit 2 (First Operative Day 0), Visit 3 (Day 1), Visit 4 (Day 10), Visit 5 (Week 4), Visit 5.1 (Month 6), Visit 5.2 (Month 12), Visit 5.3 (Month 18), Visit 6 (Pre-Exchange Exam, within 10 days prior to Visit 7), Visit 7 (Second Operative/ Exchange), Visit 8 (Day 1 PE), Visit 9 (Day 10 PE), and Visit 10 (Week 4 PE). Subjects will exit the study at the conclusion of the Week 4 PE visit.

All subjects will have visits at post-operative Day 1, Day 10, Week 4, pre-exchange, and post-exchange Day 1, Day 10, and Week 4. Table 1 summarizes the remaining visits for each cohort along with other cohort information. Appendices A-G show the schedule of visits and measurements for each cohort.

Subjects will be assigned to their cohort sequentially as defined by the cohort order as they receive surgery. Each cohort must be filled prior to starting the next cohort.

Table 1. Cohorts in the Study¹

A large black rectangular box redacting the content of Table 1.

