2.4. Sample Size Determination

The sample size of 210 subjects who undergo implantation and exchange of a Travoprost Intraocular Implant was determined to support the study objectives and is not based on statistical power calculations. [REDACTED]

[REDACTED]

3. Analysis Sets

For the purposes of analysis, the following analysis set is defined:

Subject Analysis Set	Description
Safety analysis set	
• All subjects who receive an implant.

The safety analysis set will be used for all data tabulations and listings.

4. General Statistical Considerations

Demographic and safety data collected on the case report forms (CRFs) will be displayed in tabulations and data listings. Only data from scheduled visits will be used in tabulations unless otherwise specified. In general, summary tables will be presented [REDACTED] [REDACTED]. Data may also be summarized by study period if indicated. Data listings will present data either recorded on or derived using the CRF. [REDACTED] [REDACTED]

No formal statistical testing will be performed. All data summaries [REDACTED] will be performed using SAS® software, Version 9.4 or higher.

Continuous data will be summarized using the number of observations, mean, standard deviation, median, minimum, and maximum. Continuous data may also be dichotomized, or otherwise split, into clinically meaningful categories and may be further analyzed as categorical data as specified in the individual endpoints.

Categorical data will be summarized using frequency counts and percentages. Unless otherwise stated, subjects with missing visit data will be omitted from both the numerator and denominator of such calculations.

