7.1.3.1. Visual Acuity

Best spectacle corrected visual acuity (BSCVA) is measured at Screening using the Early Treatment Diabetic Retinopathy Study (ETDRS) letter chart. Corrected VA (ETDRS) is collected at Week 4, Month 6, Month 12, Month 18, Pre-Exchange, and Week 4 PE unless a decrease of 2 or more lines (≥ 10 letters) from Screening occurs, at which time BSCVA is also measured. Pinhole VA (Snellen) is collected at the Day 1, Day 10, Day 1 PE and Day 10 PE visits.

Corrected VA and BSCVA will be presented in tabulations. If both corrected VA and BSCVA are collected, only BSCVA will be presented in the tabulations.

The worst change in VA will be summarized [REDACTED] for the total, initial, and PE study periods. The worst change in VA is defined as the largest decrease, or smallest increase if there is no decrease, in number of letters read correctly across all

postoperative visits (scheduled or unscheduled) in the study period. For the initial and total study periods, only the worst CFB will be presented. For the PE study period, the worst CFPE will also be presented. The number and percentage of subjects with a worst decrease of greater than or equal to 15 letter (3 lines) will also be summarized for each study period.

The actual and CFB in number of letters read correctly will be summarized by visit [REDACTED]. The number and percentage of subjects with a decrease of greater than or equal to 15 letters (3 lines) will also be summarized by visit [REDACTED]. For visits belonging to the PE study period, the CFPE will also be summarized both continuously and categorically as outlined.

A visual acuity subject listing will be provided for all visual acuity data including pinhole VA.

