7.1.3.2. Slit Lamp Examinations

Slit lamp measures collected on the CRF include corneal edema, corneal opacity, epithelium, endothelium, guttata, anterior chamber depth, anterior chamber cells, anterior chamber flare, and pupil. All slit lamp measures are collected at Screening and each postoperative visit within both study periods (Day 1, Day 10, Week 4, Month 6, Month 12, Month 18, Pre-Exchange, Day 1 PE, Day 10 PE, and Week 4 PE).

For each measure, the number and percentage of subjects in each severity grade/category will be summarized by visit [REDACTED].

Slit lamp findings will also be summarized by time interval within each study period. For the initial study period, the time intervals will consist of after Baseline through Week 4, after Week 4 to Month 12, and after Month 12 to Month 24. For the PE study period, only the time interval of after pre-exchange to Week 4 PE will be summarized. The summaries will include the number and percentage of subjects with at least one clinically significant worsening during the specified time interval (including data from unscheduled visits) [REDACTED]. For the initial study period, only a clinically significant worsening from baseline will be presented. For the PE study period, both a clinically significant worsening from baseline and a clinically significant worsening from pre-exchange will be presented. [REDACTED]

[REDACTED] For findings not associated with a severity grade, a status change from normal/absent to abnormal/present at any postoperative visit during the time interval will be summarized.

All slit lamp data will be listed. Two additional slit lamp listings will be provided – one for subjects with a worsening from baseline and one for subjects with a worsening from pre-exchange. For each subject, the listings will present findings at each visit only for measures with either

- (1) at least one clinically significant worsening at any follow-up visit during the study for findings associated with severity grade or
- (2) a status change (i.e., a change from normal/absent to abnormal/present at a follow up visit) at any follow-up visit during the study for findings not associated with severity grade.

Other slit lamp findings will also be listed.

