2.3. Study Design

This is a prospective, non-randomized, open-label, single center trial evaluating [REDACTED] [REDACTED] the performance of the Travoprost Intraocular Implant in subjects with open-angle glaucoma (OAG) or ocular hypertension (OHT). Approximately 210 total subjects (14 cohorts of 15 subjects) will be enrolled into the study. Subjects will be screened for qualification as per the inclusion/exclusion criteria (refer to Sections 6.2.1 and 6.2.2 of study protocol). Qualified subjects will be assigned to a cohort and will be implanted with the Travoprost Intraocular Implant (G2-TR-125 Implant) in one eye. Each cohort will consist of a specified duration [REDACTED]

[figure not shown]
[REDACTED] All enrolled subjects will undergo a second operative visit, the exchange of the Travoprost Intraocular Implant, at Visit 7. The duration of time for each cohort is the time between the implantation of the 1st implant at Visit 2 (Day 0) and the implantation of the 2nd implant at Visit 7 (Exchange procedure and collection of the aqueous humor and explant).

Depending on the cohort assignment, subjects will be followed for 4 – 25 months postoperatively (3 – 24 months after 1st implantation and 4 weeks after the 2nd implantation). Study follow-up will continue until the Week 4 post-exchange (PE) visit.

Depending on the cohort assignment, the study consists of 10 to 13 visits: Visit 1 (Screening), Visit 2 (First Operative Day 0), Visit 3 (Day 1), Visit 4 (Day 10), Visit 5 (Week 4), Visit 5.1 (Month 6), Visit 5.2 (Month 12), Visit 5.3 (Month 18), Visit 6 (Pre-Exchange Exam, within 10 days prior to Visit 7), Visit 7 (Second Operative/ Exchange), Visit 8 (Day 1 post-exchange [PE]), Visit 9 (Day 10 PE), and Visit 10 (Week 4 PE). Subjects will exit the study at the conclusion of the Week 4 PE visit.

All subjects will have visits at post-operative Day 1, Day 10, Week 4, pre-exchange, and post-exchange Day 1, Day 10, and Week 4. Table 1 summarizes the remaining visits for each cohort along with other cohort information. Appendices A-G show the schedule of visits and measurements for each cohort.

Subjects will be assigned to their cohort sequentially as defined by the cohort order as they receive surgery. Each cohort must be filled prior to starting the next cohort.

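### Study-eye TEAE percentages are tabulated for an initial period of 91 to 730 days beside a 28-day post-exchange period, and no matched 4-week window is given

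*SAP*

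**What the plan says.** SAP 2.3.1 splits all data at the exchange into an initial and a PE period. SAP 7.1.2 reports the number and percentage of subjects with TEAEs, and adds: "Tabulations of study eye TEAEs for each of the above categories will be provided for each study period". Those categories are all, related, by maximum severity, and serious. An event that begins before the exchange and continues past it stays in the initial period, unless its severity increases or its relationship to treatment changes; it is then counted in both.

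Protocol 6.3.4.7 sets the exchange at nominal days 91, 182, 365, 456, 547, 637 or 730, each ±14. Follow-up afterwards ends at Week 4 PE (28 ± 3 days); SAP 2.3 describes it as "and 4 weeks after the 2nd implantation". SAP 7.1.1 summarises exposure in days by period, but the readable text does not use it as a denominator for adverse events.

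Other measures are handled differently. For slit-lamp findings in the initial period (SAP 7.1.3.2), "the time intervals will consist of after Baseline through Week 4", followed by later intervals; the PE interval runs from pre-exchange to Week 4 PE. Lens findings (SAP 7.1.3.3) follow the same pattern. Acuity (SAP 7.1.3.1) is tabulated by visit, and also as the worst change over all "postoperative visits (scheduled or unscheduled) in the study period".

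On purpose, Protocol 8.1 says of N = 210: "This sample size is considered adequate to provide information on the safety of the exchange procedure". SAP section 4 adds: "No formal statistical testing will be performed".

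**The concern.** The two columns cover very different lengths of follow-up within every cohort, so tabulating by cohort (Protocol 8.3) does not remove the difference. The percentage of subjects with at least one event can only grow as the window lengthens. A reader who sees the periods side by side will tend to read the lower PE percentage as evidence that the exchange is no riskier than the first implantation, when part or all of the gap may come from the calendar.

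This matters because the only purpose Protocol 8.1 attaches to the sample size is information on the safety of the exchange. There is no control arm, so the first operation in the same eye is the obvious context for that information. The SAP already sets a 4-week window beside the PE interval for slit-lamp and lens findings, but not for adverse events, which head its list of safety endpoints (SAP 2.2).

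**Working it through.** **The plan's own figures.** The data analysis plan filed with the SAP (section 2.3) says "Approximately 210 total subjects (14 cohorts of 15 subjects) will be enrolled into the study": 14 × 15 = 210, which reproduces. SAP 2.4 says N "was determined to support the study objectives and is not based on statistical power calculations", so there is no power figure to check. Follow-up also reproduces: 91 + 28 = 119 days (3.9 months) and 730 + 28 = 758 days (24.9 months), against the stated 4 to 25 months.

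**Window ratio, initial to PE.** Group 3: 91/28 = 3.25. Group 24: 730/28 = 26.1.

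**TEAE percentages under equal surgical risk.** Assumptions, none of them in the documents: a 4-week risk p = 20% at both operations, a constant background h per month after the first 28 days (0.92 month), and no dropout. For an exchange at T months:

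initial % = 1 − (1 − p) × exp(−h × (T − 0.92)); PE % = p.

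Example, Group 24 at h = 1%: 1 − 0.80 × exp(−0.01 × 23.08) = 36.5%.

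| Background per month | Group 3, initial | Group 24, initial | PE, either group |
|---|---|---|---|
| 0 | 20.0% | 20.0% | 20% |
| 0.25% | 20.4% | 24.5% | 20% |
| 1% | 21.6% | 36.5% | 20% |
| 3% | 24.8% | 60.0% | 20% |

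If the seven durations are equally represented (an assumption; Table 1 is redacted), the overall initial column is about 30% at 1% per month and 45% at 3%, against 20%.

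A second set of assumptions points the same way. Take surgical risk s and annual background b, with T in days: % = 1 − (1 − s) × exp(−bT/365.25). At s = 10% and b = 0.10, Group 24 shows 26.3% and PE 10.7%. Over s = 5–20% and b = 0.05–0.20, the ratio of the seven-group mean to PE runs from 1.21 to 3.78. Cutting both windows at 28 days gives 1.00 throughout.

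**Would person-time rates help?** No, because all PE time is early post-surgical time. With p = 20%, the PE rate is 0.20/0.92 = 21.7 per 100 person-months.
- Group 24 at h = 1%: (0.20 + 0.01 × 23.08)/24 = 1.8 per 100, so the exchange looks about 12 times worse.
- Group 3 at h = 3%: (0.20 + 0.03 × 2.08)/3 = 8.7 per 100, so it looks about 2.5 times worse.

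The true risks are equal in both cases.

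**Acuity.** The appendices schedule 2 ETDRS exams in the initial period (Groups 3 and 6), 3 (Group 12), 4 (Groups 15 and 18) or 5 (Groups 21 and 24), against 1 in the PE period. I simulated no true change, with an assumed SD of 5 letters per measurement and a shared baseline. I applied the plan's rule that a fall of 10 or more letters triggers a BSCVA measurement, which replaces the first value in the tables (assumed independent, same SD).
- Mean worst change from baseline, initial: −2.1 letters (2 exams) to −4.8 (5 exams). Mean PE change from pre-exchange: 0.
- Loss of 15 or more letters: 1.3% to 2.7% initial, against 1.2% PE.

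Without the retest rule these losses would be 3.1–6.5% against 1.7%, so the rule removes more than half of the apparent initial-period losses.

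**The case against.** The strongest reply is that no comparison of the two operations is planned. The stated objective is implant performance and elution, safety is descriptive, and Protocol 8.1 promises information on exchange safety, not a contrast with first implantation. That stands: this is a risk of misreading, not a failed planned analysis.

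A reader might also infer that the two operations cannot be compared at all. The documents do not support that. Change from baseline at Week 4 and change from pre-exchange at Week 4 PE are both tabulated for acuity, including losses of 15 or more letters. Slit-lamp and lens findings have matched intervals, and IOP and gonioscopy are reported by visit. For adverse events, study days are defined from each operation (SAP 4.1.4) and every event is listed, so a matched count could be made afterwards. Intraoperative events have no window problem. Redactions in SAP 7.1.2 may also hide layout details.

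Nor is it certain that the exchange will look safer. With no events after day 28 the columns agree, and a low background is plausible: one rule in Protocol section 9 records events only if they are in the study eye and judged related, although the same section also says regardless of causality. For worst acuity, the PE period is also shown as change from baseline, which carries earlier loss forward and need not look better.

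Finally, first implantation is an imperfect reference. The exchange adds an anterior chamber tap and implant removal, and topical hypotensives are stopped at the first operation. This calls for careful labelling, but not for leaving unequal windows side by side.

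**Conclusion.** The point holds for the TEAE tables. Windows that differ 3.25-fold to 26-fold sit side by side within cohorts, and the readable text has no matched window. Given any adverse events after day 28, equal 4-week risks produce a lower PE percentage. The direction follows from the design; the size does not. Under the assumptions shown, the gap ranges from nothing (zero background), through 0.4 to 4.5 points (0.25% per month), to 40 points (Group 24 at 3% per month). The 20% risk, the background rates, their constancy and the absence of dropout are all assumptions.

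For acuity the point reduces to a caution. The matched by-visit results are already planned; only initial worst change from baseline set against PE worst change from pre-exchange misleads, and modestly once the retest rule is applied.

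This is a cheap reporting improvement that puts exchange safety in context. It does not show that the planned tables are wrong as descriptions of each period.

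**What to change.** Before database lock, add one table to SAP 7.1.2: study-eye TEAEs (all, related, severe, serious, main preferred terms) from first surgery through the Week 4 visit, beside exchange through the Week 4 PE visit. Assign events by onset date and use the same exchanged subjects in both columns. A descriptive paired difference with a 95% CI is optional; with 210 pairs and independence its half-width is 1.96 × √(2p(1 − p)/210), or ±5.7 points at 10% risk and ±7.7 at 20%.

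Footnote the table to say that:
- the contrast is first versus second surgery and is not randomised;
- the exchange also includes an anterior chamber tap and implant removal;
- subjects who exited before the exchange are left out;
- events continuing across the exchange belong to the initial period, with the SAP's exception for a change in severity or relationship handled explicitly.

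In SAP 7.1.3.1 add only a note that initial-period worst change from baseline (2 to 5 scheduled exams) should not be compared with PE worst change from pre-exchange (1 exam). Point readers to the Week 4 and Week 4 PE by-visit results instead.

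The cost is one table and a footnote, from data already collected, with no change to study procedures. Do not substitute whole-period person-time rates.
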